³⁰RMC 4630 BIW dosing should be administered PO on D1 and D2. During clinic visit days in C1, as well as D1 of subsequent cycles, RMC 4630 should be administered in the clinic in order to comply with blood PK, ctDNA, or ECG assessment timepoints.

³¹Initially, subjects will be dosed sotorasib 960 mg QD PO. If supported by the data from a post-marketing study of sotorasib dose optimization in patients with advanced NSCLC who have received 1 prior therapy, at the Sponsor's discretion, new subjects enrolling on this trial may be treated at sotorasib 240 mg QD in combination with RMC-4630. Subjects currently enrolled at 960 mg may continue at their current dose or dose reduce based on discussion with the Sponsor's Medical Monitor. Subjects developing toxicities at sotorasib 240 mg QD in combination with RMC-4630 may dose reduce to sotorasib 120 mg QD in combination with RMC-4630 or discontinue treatment. During clinic visit days in C1, as well as D1 of subsequent cycles, sotorasib should be administered in the clinic in order to comply with blood PK, ctDNA, and ECG assessment timepoints.

³²Blood samples (3 mL/sample) for RMC 4630 and sotorasib PK analyses will be obtained at the timepoints listed in [Table 2](#).

³³Blood samples (10 mL/sample) for ctDNA will be obtained at the timepoints listed in [Table 2](#).

³⁴For all subjects, archival tumor tissue collected preferably within 3 years should be submitted between screening and EOT. FFPE tissue blocks with sufficient specimen to allow sectioning for 21 × 4 micron slides are preferred. Alternatively, one H&E-stained slide with a 20 × 4 micron freshly cut specimen (with minimum 30% viable tumor volume) can be provided. Pretreatment fresh biopsies will be mandatory for subjects who do not have available archival tissue preferably from within 3 years, unless the investigator determines that the tumor site is not amenable to biopsy or poses a significant risk to subject safety. The Sponsor will evaluate this requirement on a case-by-case basis. The pre-treatment biopsy should not be collected until the subject is determined to be eligible for the study by the Sponsor. Any tumor site amenable to biopsy (excisional or needle [4 cores × 18 gauge or <18 gauge needle]) is acceptable, except for bone metastases. Acceptance of needle biopsy cores from >18-gauge needles will be evaluated by the Sponsor on a case-by-case basis and may require additional cores.

Abbreviations: AE = adverse event; ALP = alkaline phosphatase; ALT = alanine aminotransferase; AST = aspartate aminotransferase; aPTT = activated partial thromboplastin time; BIW = twice weekly; BUN = blood urea nitrogen; C = cycle; C1D1 (CxRx, etc) = Cycle 1 Day 1, etc; CPK = creatine phosphokinase; CR = complete response; CT = computed tomography; ctDNA = circulating tumor deoxyribonucleic acid; D = day; ECG = electrocardiogram; eCRF = electronic Case Report Form; ECHO = echocardiogram; ECOG = Eastern Cooperative Oncology Group; ECOG PS = Eastern Cooperative Oncology Group Performance Status; EOS = End-of-Study; EOT = End-of-Treatment; FFPE = formalin fixed paraffin embedded; FSH = follicle-stimulating hormone; GGT = gamma-glutamyl transferase; GI = gastrointestinal; HBcAb = hepatitis B core antibody; HBsAg = hepatitis B surface antigen; HCV = hepatitis C virus; H&E = hematoxylin and eosin; HEENT = head, eyes, ears, nose, and throat; INR = international normalized ratio; KRAS^{G12C} = KRAS with a mutation at codon 12, which encodes glycine (G) to cysteine (C); LVEF = left ventricular ejection fraction; MCH = mean corpuscular hemoglobin; MM = striated muscle; MRI = magnetic resonance imaging; MUGA = multigated acquisition; MCV = mean corpuscular volume; NSCLC = non-small-cell lung cancer; OCT = optical coherence tomography; PD-L1 = Programmed death-ligand 1; PET = positron emission tomography; PK = pharmacokinetics(s); PO = oral(ly); PR = partial response; PT = prothrombin time; PTT = partial thromboplastin time; QD = once daily; RBC = red blood cell; QTc = corrected QT interval; RECIST v1.1 = Response Evaluation Criteria in Solid Tumours, Version 1.1; SAE = serious adverse event; SOC = standard-of-care; WBC = white blood cell.

Table 2: PK and [REDACTED] Sampling

Cycle/EOT Study Day	PK Time Points	[REDACTED] Time Points	Collection-Time Window
C1			
	NA	[REDACTED]	NA
[REDACTED]	Predose	[REDACTED]	Within 1 hour before dose
	2 hours postdose	--	2 hours ±10 minutes after dose
C2, C3, C4			
[REDACTED]	Predose	[REDACTED]	Within 1 hour before dose
Every 3 cycles (C7, C10, C13, C16) afterward up to C16			
[REDACTED]	Predose	NA	Within 1 hour before dose
EOT	NA	X	Any time during visit
Extended- Use	NA	NA	NA

Abbreviations: C = cycle; [REDACTED]; EOT = End-of-Treatment; NA = not applicable; PK = pharmacokinetic(s).

Note: On any days that a PK specimen is collected, the subject should be administered study drug in the clinic.

[figure not shown]

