¹⁴ ECHO is the preferred methodology to measure LVEF. MUGA may be used if ECHO is not available or not technically feasible. However, the same methodology should be used throughout the study. Assessments should be performed during screening, on C2D1 (+7 days), EOT, and if clinically indicated at any point. If a subject does not complete 2 cycles of study treatment, the EOT assessment of LVEF is not required unless clinical signs or symptoms warrant an examination. All subjects who require dose reduction of study treatment due to decrease in LVEF should have ECHO at the end of each cycle for 2 more cycles and then if clinically indicated to ensure that subject is not experiencing a decrease in LVEF even with a reduced dose.

¹⁵ ECOG PS to be assessed at screening, C1D1, C1D15, and D1 of each subsequent cycle beginning at C2, and at EOT. During the Extended-Use phase, ECOG PS will be assessed according to local standards of care.

¹⁶ Ophthalmic examination if clinically indicated, including full fundoscopic examination and optical coherence tomography should be performed by an ophthalmologist. Additional examinations should be performed as clinically indicated.

¹⁷ Monitor and record AEs and SAEs throughout the main study. Record all AEs, regardless of relationship to study treatment, that occur after initiation of first study treatment until EOT. All AEs and SAEs will be collected from the start of treatment until 30 days after the last dose, or upon initiation of alternative cancer treatment, whichever occurs first. After this period, investigators should report only SAEs that are thought to be related to RMC 4630 and/or sotorasib. After informed consent, but prior to initiation of study treatment, only SAEs caused by a protocol mandated intervention will be collected (eg, SAEs related to invasive procedures such as biopsies or medication washout). All SAEs that occur should be reported to the Sponsor or designee within 24 hours of investigator awareness. All AEs (regardless of relationship to study treatment) and SAEs determined not to be study- treatment related (ie, not related and unlikely related)

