will be followed through the last study visit and be noted as “continuing” if not resolved at this visit. Any SAE that is determined to be study treatment related (possibly, probably, or definitely related) will be followed to resolution or stabilization, until it is determined to be irreversible by the investigator, the subject is lost to follow up, or it has been determined that the study treatment is not the cause of the AE/SAE. AE/SAE reporting will end after the subject initiates alternative cancer treatment. During the Extended-Use phase of the study, only SAEs (irrespective of causality) and related AEs will be reported in the EDC. All SAEs will also be reported on the SAE Report Form.

¹⁸ Record all concomitant medications including any prescription medications, over the counter preparations, and transfusions received by subject from 7 days preceding C1D1 through EOT. During the Extended-Use phase, concomitant medications given for SAEs only will be recorded.

¹⁹ Subjects should be instructed to bring their pills and diary to every clinic visit, or to submit diary information at that time.

²⁰ Hematology includes the following: RBC count, hemoglobin, hematocrit, MCV, MCH, % reticulocytes, platelet count, WBC count, and differential (neutrophils, bands [if available], lymphocytes, monocytes, eosinophils, basophils, other cells). NOTE: Testing must be performed and reviewed before dosing on C1D1. If hematology samples are obtained within the previous 72 hours as part of screening, then re-testing on C1D1 is not required. For subsequent visits after C1D1, samples may be obtained up to 72 hours prior to the visit. During the Extended-Use phase, hematology testing will be performed according to local standards of care.

²¹ Serum chemistry includes the following: sodium, potassium, chloride, bicarbonate/carbon dioxide, BUN, creatinine, glucose (non-fasting), albumin, total protein, calcium, magnesium, phosphorus, uric acid, lipase, GGT, ALT, AST, total and direct bilirubin, and ALP. NOTE: Perform tests and review results before dosing on C1D1. If chemistry samples were obtained within the previous 72 hours as part of screening, then re-testing on C1D1 is not required. Plasma is permitted. For subsequent visits after C1D1, samples may be obtained up to 72 hours prior to the visit. During the Extended-Use phase, serum chemistry testing will be performed according to local standards of care.

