8.3.1. Time Period and Frequency for Collecting AE and SAE Information

Monitoring and recording of AEs and SAEs will be conducted throughout the study. After the signing of the ICF, but prior to initiation of study treatment, only SAEs caused by a protocol-mandated treatment will be collected (eg, SAEs related to invasive procedures, such as biopsies or medication washout). Any medical occurrence that begins before the start of study treatment but after obtaining informed consent, and which is not considered an SAE caused by a protocol-mandated treatment, will be recorded on the Medical History/Current Medical Conditions Section of the eCRF rather than the AE section.

All AEs and SAEs will be collected from the start of treatment until 30 days after the last dose, or upon initiation of alternative cancer treatment, whichever occurs first. After this period, investigators should report only SAEs that are thought to be related to RMC-4630 and/or sotorasib.

Any SAE that is determined to be study-treatment related (possibly, probably, or definitely related) will be followed to resolution or stabilization, until it is determined to be irreversible by the investigator, the subject is lost to follow-up, or it has been determined that the study treatment is not the cause of the AE/SAE, whichever occurs first. After this period, investigators should report only SAEs that are thought to be related to RMC-4630 and/or sotorasib.

All SAEs will be recorded and reported to the Sponsor or designee within 24 hours of investigator awareness, as indicated in [Appendix 3](#). The investigator will submit any updated SAE data to the Sponsor within 24 hours of it being available. During the Extended-Use phase of the study, only SAEs (irrespective of causality) and related AEs will be reported in the EDC. All SAEs will also be reported on the SAE Report Form.

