8.3.3. Follow-Up of AEs and SAEs

After the initial AE/SAE report, the investigator is required to proactively follow each subject at subsequent visits/contacts through the last study visit. All AEs (regardless of relationship to study treatment) and SAEs determined not to be study-treatment related (ie, not related and unlikely related) will be followed through the last study visit and be noted as “continuing” if not resolved at this visit.

All SAEs considered study-treatment related (possibly, probably, or definitely related) will be followed until resolution, stabilization, is determined to be irreversible by the investigator, the subject is lost to follow-up (as defined in [Section 7.3](#)), or it has been determined that the study

treatment is not the cause of the AE/SAE, whichever occurs first. The investigator will submit any updated SAE data to the Sponsor within 24 hours of it being available. During the Extended-Use phase of the study, only SAEs (irrespective of causality) and related AEs will be reported in the EDC. All SAEs will also be reported on the SAE Report Form. Reporting of AEs/SAEs will end after the subject initiates alternative cancer treatment.

Further information on follow-up procedures is given in [Appendix 3](#).

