7.7 Safety Analyses

Safety endpoints of the study are the incidence, nature, and severity of treatment-emergent adverse events (TEAEs), SAEs, clinical laboratory tests, vital signs, and ECGs.

Adverse events (AEs) will be collected from the date that informed consent was signed. Verbatim terms for each AE will be coded using MedDRA Version 25.0 or later and graded per the NCI CTCAE Version 5.0 or later. Treatment-emergent adverse event (TEAE) is defined as those AEs with an onset on or after the date of the first dose of study intervention and within 30 days of last known dose of study intervention. Treatment-related AEs are treatment-emergent AEs reported as related to RMC-4630 or sotorasib.

All AE summaries will be presented for the initial combination dose level and overall using the treated population.

Safety Stopping Rules

During dose expansion after the final expansion dose has been selected, evaluation of all Grade 4 or higher treatment-related adverse event rates will be conducted to assess if the unacceptable toxicity threshold has been reached. If this threshold is met, enrollment to dose expansion will be halted pending review of safety data. After reviewing the totality of data from both CodeBreaK 101C and cumulative data from this study, one of the following actions may be taken:

1. Terminate the study
2. Amend the protocol to potentially improve the benefit/risk for subjects (e.g., increase safety monitoring, modify dose/schedule, mandate premedication)
3. Continue dose expansion without any changes

The stopping rules use a Bayesian approach to pause the enrollment if the posterior probability is $\geq 80\%$ that the Grade 4 or higher treatment-related adverse event rate is greater than 20%. The stopping boundaries shown in Table 1 assume a prior distribution of Beta (0.4, 1.6). The operating characteristics with the pre-specified batch size of 10 new subjects are summarized in Table 2.

Table 1: Stopping Boundary by Number of Subjects

Number of Subjects Treated	Number if Subjects with Grade 4 or Higher Treatment Related Adverse Events to Halt Enrollment
10	≥ 4
20	≥ 6
30	≥ 9
40	Expansion Complete

Table 2: Operating Characteristics of Stopping Rules

True Grade 4 or Higher Treatment-Related Adverse Event Rate	Probability of Early Stopping of Dose Expansion	Average Dose Expansion Sample Size
0.1	2.1%	39
0.15	9.7%	38
0.2	25.8%	34
0.25	47.7%	29
0.3	69.2%	23

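### The protocol gives contradictory rules for when AE/SAE collection stops: related SAEs after new cancer therapy, and AEs between an early EOT visit and day 30, may or may not be reported

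*Protocol*

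**What the plan says.** Protocol Table 1, footnote 17, contains four statements about when collection ends:

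- A. "Record all AEs, regardless of relationship to study treatment, that occur after initiation of first study treatment until EOT".
- B. In the next sentence, all AEs and SAEs are collected "until 30 days after the last dose, or upon initiation of alternative cancer treatment, whichever occurs first".
- C. Once that period is over, SAEs thought to be related to either drug are still to be reported.
- D. Further on, "AE/SAE reporting will end after the subject initiates alternative cancer treatment".

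Section 8.3.1, the section devoted to the collection period, repeats B ("All AEs and SAEs will be collected from the start of treatment until 30 days after the last dose", or to new therapy if earlier) and C ("After this period, investigators should report only SAEs that are thought to be related to RMC-4630 and/or sotorasib"). It does not name EOT as an end point. Section 8.3.3 repeats D: "Reporting of AEs/SAEs will end after the subject initiates alternative cancer treatment".

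The EOT visit is due within 30 days of the last dose (footnote 2; Sections 4.1.1 and 7.1), or before any new antitumor treatment (Section 7.2). Section 7.2 then counts the subject as having finished the study.

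SAP 7.7 counts as treatment-emergent any AE with onset from first dose and "within 30 days of last known dose of study intervention". It makes no cut at EOT or at new therapy. It defines treatment-related AEs as a subset of these.

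**The concern.** Statements C and D cannot both be followed. B allows new therapy to close the window, and C then requires related SAEs to be reported; D forbids it. A and B also disagree whenever the EOT visit takes place before day 30.

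TEAEs and SAEs are a secondary endpoint. SAP 7.7 will present a 30-day post-dose window as if it had been observed in full, although sites obeying A or D would have stopped collecting earlier. Different sites, about 40 in all (Protocol 4.1), could each comply with the protocol and still collect over different periods. The SAP's count of treatment-related AEs of Grade 4 or higher, on which the expansion stopping rule depends, draws on the same reports. Late related SAEs also matter for the sponsor's safety reporting, whether or not they enter a table.

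**Working it through.** No sample-size, power or event-rate figure underlies this point, so there is no plan figure to reproduce. The check sets the rules side by side and does day arithmetic on them.

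**Inputs.** Day 0 is the last dose. Let t be the day of the EOT visit, 0 ≤ t ≤ 30 (footnote 2). Let s be the day new therapy starts, if it does; Section 7.2 places EOT before it, so t ≤ s.

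**EOT cut-off against the 30-day window, no new therapy by day 30.** A stops at day t and B at day 30. Days in dispute = 30 − t:

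- t = 0: 30 − 0 = 30 days
- t = 14: 30 − 14 = 16 days
- t = 30: 30 − 30 = 0 days

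The range is 0 to 30 days. The documents give no distribution of t, so no average can be stated.

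**New therapy on day s.** Under C, related SAEs after day s are reportable with no end date. Under D, none is. The disputed period is open-ended.

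**SAP window against protocol collection, s < 30.** B closes general AE collection at day s, while the TEAE window runs to day 30. The SAP window therefore extends 30 − s days beyond collection; for s = 21, that is 30 − 21 = 9 days. This mismatch arises even at a site that follows Section 8.3.1 exactly.

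**Worked illustration.** Assume, only to show the effect, t = 7 and s = 21:

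| Event | Rules that capture it | Rules that do not | In SAP TEAE window? |
|---|---|---|---|
| Non-serious AE, day 10 | B | A | Yes |
| Non-serious AE, day 25 | None | A, B, D | Yes |
| Related SAE, day 25 | C | D | Yes |
| Related SAE, day 40 | C | D | No |

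**Is there a tie-breaker?** For A against B, the balance of the text favours B: the next sentence of footnote 17, Section 8.3.1 and the SAP all point to 30 days. For C against D there is none. Footnote 17 holds both, Section 8.3.1 supports C and Section 8.3.3 supports D. Limiting D to the Extended-Use phase does not work either: in Section 8.3.3 it follows the Extended-Use text, but in footnote 17 it comes before it.

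**Would a scheduled contact pick up events after an early EOT visit?** In Table 1 the main-study AE row has an entry at EOT/EOS and none under LTFU. The later contact is a telephone call about survival, which SAP 2.2.3 places every 3 months and which also documents anticancer treatment. Neither document describes it as an AE enquiry.

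**The case against.** The strongest reply is that the protocol already contains a workable rule. The 30-day limit and the new-therapy limit are not rivals: they form one rule, ending at whichever comes first, and footnote 17 carries it as well as Section 8.3.1. A site that follows Section 8.3.1 collects to day 30 however early EOT falls. SAEs are reportable within 24 hours of the investigator's awareness, not only at visits, and related SAEs already identified are followed to resolution or stabilization. Ending routine AE collection at new therapy is a legitimate choice. The safety analysis is descriptive, with no hypothesis test.

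Much of that stands, and it limits what may be concluded. A reader might infer that up to 30 days of AEs will be lost and that TEAE rates are therefore biased downwards. The documents do not support that as a fact: it requires the EOT phrase to override the sentence after it, Section 8.3.1 and the SAP. Loss is a risk that depends on site practice, although any error from it would lower the counts.

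A reader might also infer that dropped late SAEs distort the safety endpoint. Beyond day 30 they do not, because SAP 7.7 excludes them from the TEAE and treatment-related tables under either rule. Only events up to day 30 can affect those tables or, through the SAP's definition, the stopping-rule count.

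What the reply does not answer is the conflict between continued reporting of related SAEs and the unqualified stop at new therapy.

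**Conclusion.** The concern holds as an internal contradiction in the protocol, with two parts. The direct one is whether related SAEs remain reportable after new therapy starts: footnote 17 says both yes and no, and Sections 8.3.1 and 8.3.3 take opposite sides. The second is the EOT cut-off in footnote 17, which conflicts with every other statement of the window and puts 0 to 30 post-dose days in doubt, according to when the visit happens. A related gap lies between the documents: the SAP's TEAE window outlasts collection by 30 − s days when new therapy starts on day s before day 30.

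The size in events cannot be estimated, because neither document gives the timing of EOT visits, the share of subjects starting new therapy within 30 days, or late event rates. The conclusion assumes only that some sites will follow the sentences that stop collection earlier. It should be corrected, because the text is wrong as written and the remedy is small.

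**What to change.** Reconcile footnote 17, Section 8.3.1 and Section 8.3.3 to one rule:

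1. In footnote 17, delete the EOT cut-off and rely on the existing window of 30 days or new therapy, whichever is earlier.
2. In footnote 17 and Section 8.3.3, limit the sentence that ends reporting at new therapy to events not considered related, so that it agrees with the related-SAE sentence already in footnote 17 and Section 8.3.1.
3. In Section 7.2, make clear that completing the study at the EOT visit does not end AE collection before day 30.
4. In SAP 7.7, state how the TEAE window is handled when new therapy starts before day 30: either cut at that date to match collection, or kept at 30 days with a note that general AEs were not collected after new therapy.

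A telephone AE check at day 30 for subjects whose EOT visit was earlier would help to make the window observed in practice, but it is optional; steps 1 to 3 remove the contradiction without it.

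The cost is a few sentences in the protocol and one in the SAP. The protocol part is an amendment, which under Appendix 1 needs IRB/IEC approval before implementation, across about 40 sites. No design or sample-size change is involved.

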2. INTRODUCTION

2.1. Background

2.1.1. RMC-4630

SHP2 is a non-receptor protein tyrosine phosphatase and scaffold protein that functions downstream of multiple RTKs, integrating cell surface growth factor signals to promote RAS activation [Figure 2](#). RMC-4630 was designed as a potent and selective SHP2 allosteric inhibitor that suppresses RAS activation and the proliferation in cancers that, distinct from those dependent on oncogenic RTKs, are driven by nucleotide cycling oncogenic point mutations (eg, *KRAS*^{G12C}) and wild-type amplification of *KRAS* and other RAS-GTP dependent downstream mutations, eg, *NF1*^{LOF}, or RAS-GTP dependent oncogenic *BRAF* Class 3 ([Wong, 2018](#); [Fedele, 2018](#)).

Figure 2: The RAS Signaling Pathway Demonstrating the Convergence Nodal Position of SHP2 in the Pathway

SHP2 is a convergent node for RTK to RAS signaling and regulator of RAS-GTP loading. SHP2 inhibition modulates RTK signal transduction as well as RAS signaling pathway hyperactivation driven by specific oncoproteins. Preclinical studies demonstrated that daily PO administration of RMC-4630 alone achieved dose-dependent tumor cytostasis, and in some instances, tumor reductions, in multiple CDX models bearing RAS signaling pathway activating mutations of interest: NSCLC NCI-H358 *KRAS*^{G12C}, pancreatic ductal adenocarcinoma (PDAC) MIA PaCa-2 *KRAS*^{G12C}, NSCLC NCI-H2122 *KRAS*^{G12C}, NSCLC NCI-H1838 *NF1*^{LOF}, and melanoma MeWo *NF1*^{LOF} ([Nichols, 2017](#); [Nichols, 2018](#)). RMC-4630 also significantly inhibited tumor growth in 2 PDX models of NSCLC in athymic nude mice: LUN#023 bearing *BRAF* Class 3 (*BRAF*^{D594N}) and LUN#037, which carries *BRAF*^{N581D}, a known Class 3 variant position (see current RMC-4630 Investigator's Brochure [IB]).

RMC-4630 is a potent, selective, and orally bioavailable SHP2 allosteric inhibitor that is being developed for patients with tumors harboring certain activating genotypic aberrations in the RAS signaling pathway. In this study (Protocol RMC-4630-03), RMC-4630 will be studied in combination with sotorasib, a *KRAS*^{G12C} inhibitor, in locally advanced or metastatic NSCLC

subjects with $KRAS^{G12C}$ mutation after failure of prior standard therapy to determine the efficacy, safety, tolerability and PK profile of the combination.

Preclinical data demonstrate that the potency of $KRAS^{G12C}$ inhibitor treatment can be modulated by upstream RTK activation (Lito, 2016), which occurs as an adaptive response to inhibition of $KRAS^{G12C}$ OFF state with either sotorasib or adagrasib. Concurrent inhibition of RTK signaling can optimize RAS pathway signaling in $KRAS^{G12C}$ tumors (Lito, 2016; Canon, 2019). The addition of a SHP2 inhibitor like RMC-4630 to $KRAS^{G12C}$ OFF state inhibitors improves tumor responses in preclinical models (Hallin, 2020; Liu 2018) can also abrogate $KRAS$ signaling, eliminate residual or bypass upstream RTK activity, and thereby lead to greater combinatorial efficacy as well as deeper and more durable responses.

Most patients with mutations/rearrangements that confer hyperactivation of the RAS signaling pathway have a poor prognosis. RMC-4630 is currently being studied in the clinic as a monotherapy and in combination with several agents, including cobimetinib (MEK inhibitor), pembrolizumab (checkpoint inhibitor), osimertinib (RTK inhibitor), and sotorasib ($KRAS^{G12C}$ OFF state inhibitor). A first-in-human, Phase 1 dose-escalation and expansion study (RMC-4630-01; NCT03634982) established a recommended phase 2 dose (RP2D) and schedule (RP2DS) of [REDACTED] on a [REDACTED] schedule on 23 October 2020. As of 16 November 2020, [REDACTED] subjects had been treated with RMC-4630 monotherapy. The median age reported for this subject population is 63 years (range: 24.0 to 86.0 years), median prior systemic therapies is 3 (range: 0 to 11) with 69% having received 3 or more prior systemic therapies. A majority (61.5% [64/104]) of enrolled subjects have an Eastern Cooperative Oncology Group (ECOG) score of 1. [REDACTED]

Median treatment duration [REDACTED]

(range: 0 to 15.6 months). [REDACTED]

[REDACTED]. Therefore, the clinical activity observed in $KRAS^{G12C}$ mutant NSCLC is encouraging and warrants further exploration in combination studies with $KRAS^{G12C}$ OFF state inhibitors. As mentioned above, there is an ongoing study of RMC-4630 and sotorasib, which is also evaluating the safety and efficacy of this combination and is sponsored by Amgen.

RMC-4630 has been extensively evaluated in nonclinical studies to characterize its safety profile; the results of these studies support entry into clinical study. The following potential risks are based on emerging clinical data from the RMC-4630-01 (monotherapy) and RMC-4630-02 (combination) clinical trials: edema, diarrhea, anemia, and thrombocytopenia.

[REDACTED] More detailed information about the expected

benefits and risks and expected AEs of RMC-4630, based on clinical and preclinical data and drug class are in the current RMC-4630 IB, as well as in [Section 2.2.1](#).

In summary, the preclinical and clinical findings reveal potential therapeutic approaches that use a potent SHP2 inhibitor in combination with another in-pathway inhibitor to counteract the evolution of resistance in tumors harboring alterations in the RAS signaling pathway. Additionally, the combination of SHP2 inhibition with sotorasib has the potential to provide therapeutic benefit in tumors driven by oncogenic mutations insensitive to either agent alone.

